9.3.4.2 Count Data

The number of new lesions of each of the three types of lesions will be counted for all subject, regardless of which types of lesions the subject had at baseline. The definition of a new lesion is a lesion that is > 0 mm at the end-of-treatment MRI, but was non-detectable at baseline.

The number of disappearing lesions of each of the three types of lesions will be counted for all subject with at least one lesion of that type that is > 0 mm at baseline. The definition of a disappearing lesion is a lesion that is detectable at baseline, but is non-detectable at end-of-treatment.

The number of new and disappearing lesions will, for each type of lesion, be summarised as categorical variables.

The analysis of the number of new lesions will be performed for each of the three types of lesion and for endometriosis (endometrioma and DIE). It will be analysed using a negative-binomial regression with log link function.

The analysis of the number of disappearing lesions will be performed for each of the three types of lesion and for endometriosis (endometrioma and DIE). It will be analysed using a negative-binomial regression with log link function, using the number of lesions of that type as off-set.

The treatment differences between active treatment versus placebo will be reported as rate ratios with 95% confidence intervals and corresponding p-values for each of these endpoints.

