4.2.2 Randomisation

At the RM+7 visit (visit 2) of cycle -1, eligible subjects will be randomised in a 2:1 ratio to quinagolide vaginal ring dose load 1080 µg or placebo vaginal ring, administered once per menstrual cycle and sequentially for four menstrual cycles (cycles 1, 2, 3 and 4).

An independent statistician will create a computer-generated randomisation list and randomisation is performed centrally through the Interactive Response Technology (IRT) system prior to the insertion of the first vaginal ring. Thereby each subject will receive a unique randomisation number generated in the IRT system. Randomisation is stratified by site.

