9.6.3 Secondary Endpoints

The percentage change in the sum of lesion sizes by type, will be analysed using a similar ANCOVA model as the primary endpoint, but both the baseline and the cycle 4 / end-of-treatment results will be log transformed prior to analysis. The estimated difference between treatment groups will be back transformed to ease interpretation.

Secondary endpoints related to proportion of lesions and proportion of subjects with a decrease in a size of ≥ 5 mm at cycle 4 will be based on all lesions ≥ 10 mm at baseline and will be analysed using logistic regression for binary data with logit link function. The generalised estimating equation (GEE) approach will be used to account for correlated data where appropriate.

Count data related to the number of new / disappearing lesions by type, based on all lesions, will be analysed with repeated measures negative-binomial regression using a GEE approach. The regression analysis will be performed with log link function using the appropriate off-set.

Changes from baseline in the volume of endometrioma/DIE lesions assessed by MRI at cycle 4 and in the sizes of endometrioma assessed by TVU at cycle 4 will be analysed similarly to the primary endpoint, but sensitivity analyses will not be performed for these secondary endpoints.

Secondary endpoints related to PROs (B&B, NRS and EHP-30) and endocrine parameters will be analysed using a repeated measures ANCOVA model, with the change from baseline at each post-baseline time point as the dependent variable, the baseline value as a covariate, and the treatment group and treatment by time as fixed effect. The error-covariance matrix will be unstructured.

Changes in the menstrual bleeding pattern will be analysed by investigating the time to first event of change in bleeding pattern using the proportional odds regression model.

Plasma concentration of quinagolide and its metabolites will be analysed descriptively. A population pharmacokinetic modelling method will be outlined in a modelling analysis plan under the responsibility of the Translational Medicine Department of Ferring Pharmaceuticals A/S and the results will be reported separately.

All analyses and respective definitions of the endpoints will be further detailed in the SAP.

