In addition to MRI, a TVU should be performed at the screening RM+7 visit to assess uterus, endometrium, and ovaries and to measure the size(s) of any endometrioma and/or fibroid.

Subjects will be required to use a non-hormonal single-barrier method for contraception (i.e. condom) from screening to end-of-treatment.

Treatment: Eligible subjects in each sub-group will be randomised at the end of cycle -1 in to receive quinagolide vaginal ring or placebo vaginal ring for four menstrual cycles (cycles 1, 2, 3 and 4). The study was planned to be have a randomisation ratio of 2:1 with 2 subjects receiving quinagolide vaginal ring for each subject receiving placebo vaginal ring, however it was discovered, after LPLV but before database lock, that the randomisation list used during the study had a 1:1 ratio between quinagolide vaginal ring and placebo vaginal ring. Approximately 24 subjects will be

randomised in each sub-group, adding up to a total of 72 subjects in this trial. Quinagolide vaginal ring contains a dose load of quinagolide 1080 µg at a target daily release rate of quinagolide 13.5 µg.

After randomisation, subjects will self-insert the assigned ring in the upper part of the vagina at sites by following standard instructions for use. Supervision by the site staff can be provided if needed. After insertion, the vaginal ring will be kept in the vagina continuously for one menstrual cycle until being replaced by the next ring at RM+7 visit of the next cycle.

Subjects who have discontinued during or after cycle 2 should come for an end-of-treatment visit with MRI, scheduled within 2 weeks of discontinuation. Subjects who have completed the scheduled treatment should come for an MRI examination at or close to the RM+7 visit of cycle 4. The MRI at end-of-treatment / cycle 4 must be performed using the same machine, following the same procedures and sequences as at screening (detailed in the MRI manual).

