3.2 Data presentation

Due to the trial design including separate analysis of the primary endpoint for each of the three types of lesion (endometrioma, DIE and adenomyosis), some presentations will be performed by type of lesion, some will be performed for the three types of lesions combined, and some will be performed both by type and combined. Additionally, some presentations are also prepared by type of disease (i.e. endometriosis and adenomyosis), where the category of endometriosis combines endometrioma and DIE.

A subject will be included in the by type analysis if she has at least one lesion of that type ≥ 10 mm at baseline. Notice that a subject can be included in the analysis of more than one type of lesions.

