9.3.4.1 Binary Endpoints

Secondary endpoints related to proportion of lesions with a decrease in a size of ≥ 5 mm at cycle 4 and proportion of subjects with a lesion of any type that decreased in a size of ≥ 5 mm at cycle 4 will be based on all lesions ≥ 10 mm at baseline.

The proportion of lesions with a decrease as defined above and the proportions of subjects with at least one lesion decreased as defined above will be summarised

The proportion of lesions will be analysed using logistic regression for binary data with logit link function, the generalised estimating equation (GEE) approach will be used to account for correlated data (multiple lesions in one subject), and the analysis will be adjusted for baseline lesion size. The analyses will be performed for each of the three types of lesions, and for endometriosis (endometrioma and DIE).

The proportion of subjects will be analysed using logistic regression for binary data with logit link function, and the analysis will be adjusted for the number of lesions ≥ 10 mm at baseline. The analyses will be performed for the three types of lesions combined.

Menstrual bleeding pattern will be analysed by looking at the first occurrence of change from baseline (visit 2) in the amount of menstrual flow (either to a more heavy flow or to a more mild flow). This will be analysed using the proportional odds regression model. The analyses will be performed for each of the three types of lesions, and for endometriosis (endometrioma and DIE).

The treatment differences between active treatment versus placebo will be reported as odds ratios with 95% confidence intervals and corresponding p-values for each of these endpoints.

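### The new-lesion model pools women with and without the lesion type but has no baseline term: valid on average, yet open to chance imbalance and somewhat less precise than it could be

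*SAP*

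**What the plan says.** SAP 9.3.4.2 (Count Data) counts new lesions of each type in every woman: they are "counted for all subject, regardless of which types of lesions the subject had at baseline". On the model it says "It will be analysed using a negative-binomial regression with log link function". It names no covariate and no offset, and the result is reported as a rate ratio with 95% confidence interval and p-value.

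The SAP's other lesion models carry a baseline term:
- Disappearing lesions (9.3.4.2): "using the number of lesions of that type as off-set".
- Proportion of women with a shrinking lesion (9.3.4.1): "the analysis will be adjusted for the number of lesions ≥ 10 mm at baseline". The per-lesion model in the same section adjusts for baseline lesion size.
- The ANCOVAs for summed size (9.2.1) and the models built on them: the baseline value.

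Protocol 9.6.3 treats new and disappearing lesions together: "The regression analysis will be performed with log link function using the appropriate off-set". The SAP defines an offset for disappearing lesions only, and its section 12 on deviations does not comment.

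On allocation, protocol 4.2.2 states "Randomisation is stratified by site". SAP 3.1, like protocol 3.1.2, also says "Eligible subjects in each sub-group will be randomised at the end of cycle -1", but no sub-group stratum is defined.

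On population, SAP 3.2 has a general rule that a woman is "included in the by type analysis if she has at least one lesion of that type" of at least 10 mm at baseline. SAP 6.1 defines the by-type full analysis sets on the same principle, and SAP 9.3 runs the secondary analyses on the full analysis set.

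**The concern.** Whether a woman already has a lesion type, and how much of it, is a plausible predictor of new lesions of that type. The new-lesion model is the by-type lesion analysis with the most mixed population, because it deliberately includes women who never had the type, and it alone ignores baseline status. If rates differ by baseline status and the arms happen to hold unequal numbers of affected women, part of the observed rate ratio reflects who was affected and not the drug. Variation between women that could be explained also goes into the dispersion parameter and widens the interval.

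New lesions are how the trial captures progression (protocol 3.5.2), and the trial aims to identify the lesion type that responds best (protocol 3.5.1). A distorted by-type ratio could therefore mislead.

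**Working it through.** **Inputs from the documents.** Planned N = 72 (SAP 3.3; the number actually randomised is not given). Allocation 1:1 as actually used (SAP 3.1), so 36 per arm. Two-sided 5% tests.

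**Assumptions.** 24 women have the type (the planned sub-group size; more if many women have several types). New lesions per woman over treatment: r1 with the type, r0 without. Site strata are ignored.

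**Plan's own figure.** There is none for new lesions. The only design figure, 83% power for the primary comparison (16 and 8 women, 6 mm, SD 4.5 mm), reproduces as 83.7% (noncentral t, 22 df) and does not bear on the counts.

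**1. Imbalance.** The number x of affected women in one arm is hypergeometric: mean 36 × 24/72 = 12; variance 36 × (24/72) × (48/72) × (36/71) = 4.06; SD 2.01. A split of 14/10 or worse, in either direction, has probability 45%; 16/8 or worse, 8%. With 36 affected women the SD is 2.14, and gaps of at least 10 and 20 percentage points have probabilities 48% and 10%.

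**2. Expected rate ratio with no drug effect.** RR = [x·r1 + (36 − x)·r0] / [(24 − x)·r1 + (12 + x)·r0]. At 0.5 and 0.05:
- x = 14: (7.0 + 1.1)/(5.0 + 1.3) = 8.1/6.3 = 1.29.
- x = 16: (8.0 + 1.0)/(4.0 + 1.4) = 9.0/5.4 = 1.67.

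**3. Precision.** SE² of log RR = (1/36 + 1/36)(1/μ + k), with p = 1/3, μ = p·r1 + (1 − p)·r0 and k = p(1 − p)(r1 − r0)²/μ². A baseline-presence term removes k. At 0.5 and 0.05: μ = 0.2 and k = (2/9)(0.2025)/0.04 = 1.125. SE is √(0.0556 × 6.125) = 0.583 without the term and √(0.0556 × 5) = 0.527 with it, so the interval is 11% wider without.

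| r1 / r0 | RR at 14/10 | RR at 16/8 | SE without | SE with | Wider, formula | Wider, simulation |
|---|---|---|---|---|---|---|
| 0.2 / 0.02 | 1.29 | 1.67 | 0.870 | 0.833 | 4% | 1% |
| 0.5 / 0.05 | 1.29 | 1.67 | 0.583 | 0.527 | 11% | 6% |
| 1.0 / 0.05 | 1.34 | 1.81 | 0.484 | 0.389 | 24% | 20% |
| 0.5 / 0.25 | 1.09 | 1.18 | 0.417 | 0.408 | 2% | 0.5% (36 affected) |
| 0.3 / 0.3 | 1.00 | 1.00 | 0.430 | 0.430 | 0% | not run |

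The ratios shrink as more women have the type. With 48 affected, a 26/22 split gives 1.07 to 1.17 over the unequal rates.

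**4. Simulation.** Negative-binomial fits with and without a presence term, 600 trials per row. Trials with an empty arm, or with no new lesions among women without the type, were dropped: 248 of 600 at 0.2/0.02, 53 of 600 at 0.5/0.05 and at 1.0/0.05, none at 0.5/0.25.
- Mean unadjusted log RR lay between −0.003 and 0.026.
- Unadjusted rejection under the null was 0.6% to 6.6%. The Monte Carlo SE around 5% is √(0.05 × 0.95/547) = 0.9 points, so 6.6% is 1.7 SE above 5%.
- In the first three rows, log RR moved by 0.12 to 0.15 per woman above an even split without the term, and by −0.002 to 0.015 with it. In the fourth, 0.047 fell to 0.008.

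**5. Count covariate, log(n + 1).** Assumed: baseline count 1 + Poisson(1) in affected women, negative-binomial shape 2. At 0.4 new lesions per baseline lesion and 0.03 in unaffected women, the SD of log RR is 0.723 without and 0.635 with the covariate (variance ratio 1.30). At 0.1 and 0.01 the median SE is about 1.0 either way. At 0.05 and 0.01 the adjusted estimate is unstable.

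**The case against.** The strongest reply is that nothing here is invalid. Chance imbalance moves every unadjusted estimate and the confidence interval exists to cover it. This stands. A reader might infer that the rate ratio is biased or the type I error inflated; the simulation supports neither.

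The sizes depend on chosen rates. This also stands. The documents give no rates, and protocol 3.5.2 describes slowly changing disease. When new lesions are rare the gain in precision vanishes, and the adjusted model becomes fragile: in one set of 400 trials at 0.1 and 0.01 per lesion it failed to converge in 13%. A yes/no indicator is not safer. At a rate of 0.03 with shape 2, the 48 women without the type have no new lesion in (1.015)^−96 = 24% of trials, and the indicator is then separated.

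The sub-group wording could mean that randomisation was stratified by sub-group. If so, DIE would be largely balanced, because it ranks first; the exceptions are lesions below the eligibility size and women moved on when a sub-group was full (protocol 7.1.1). But sub-group means the rarest type present. A woman with DIE and endometrioma counts as DIE, so presence of endometrioma or adenomyosis would still not be balanced.

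If SAP 3.2 and the by-type sets in 6.1 govern, women without the type are not pooled. The specific sentence in 9.3.4.2 is the more natural rule for this endpoint, but the conflict is real. Baseline number of lesions would be unadjusted under either reading.

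The comparison with disappearing lesions is loose: that offset is an at-risk denominator, and a log-count offset is undefined for a woman with no lesions. Likewise, a reader might infer that the SAP broke a protocol commitment. The protocol asks only for an appropriate offset without defining it, so that does not follow.

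**Conclusion.** The point holds as an efficiency and robustness improvement, not as an error of validity. The model has no baseline term in a population that mixes affected and unaffected women, and stratification by site does not balance lesion type. If rates depend on baseline disease, the realised ratio shifts with the imbalance: 1.09 to 1.34 at a 14/10 split and 1.18 to 1.81 at 16/8, over the unequal rates tried, with 24 of 72 women affected. If rates do not depend on baseline disease, nothing shifts. The widening comes from unexplained differences between women and not from the imbalance itself. It runs from about 0% with rare events to about 20-24% at 1.0 versus 0.05.

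The endpoint is secondary and outside the Hochberg family, so a reader should not infer any effect on the primary conclusion.

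**What to change.** Amend SAP 9.3.4.2 before the blind is broken; a covariate added after an imbalance is seen would look chosen to suit it.

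1. Settle the population first. State whether the new-lesion analysis includes all treated women or only the by-type full analysis set, and reconcile 9.3.4.2 with SAP 3.2, 6.1 and 9.3. In the by-type set a presence indicator would be constant, so only a count covariate could add information.
2. Prespecify one baseline covariate for the lesion type: either log(number of lesions of that type detected at baseline + 1) or presence yes/no. For adenomyosis use presence yes/no, because diffuse disease is measured by junctional-zone thickness and has no lesion count. For the endometriosis analysis take endometrioma and DIE lesions together.
3. State that the unadjusted model is reported if the adjusted one does not converge or the covariate is separated, that is, if women without the type have no new lesions.

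The cost is a few sentences. The baseline MRI already records measurable lesions and the existence of smaller ones (protocol 7.1.1). The downside is one extra parameter when events are few, which the third item covers.

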At screening, every measurable lesion (defined as ≥ 10 mm in size) of any type should be recorded and should be summed up by type for primary analysis. For DIE and endometrioma, lesions will be measured both in size and in volume. For uterine fibroid, only size will be measured. Size will be recorded in mm as the longest diameter in the plane of measurement. Volume will be recorded in mm^3 using a semi-automated method based on 3D region-growing algorithm, adjusted with manual correction. For adenomyosis, the maximum junctional zone thickness (applicable to diffuse adenomyosis) or the size of the largest focal lesion (applicable to focal adenomyosis) will be

measured. The MRI used as baseline at screening should not be obtained more than 1 menstrual cycle before randomisation.

The central reading of MR images will be performed by two radiologists independently. In case of disagreement with regard to inclusion criterion no. 6, the opinion of a third radiologist will be sought and will determine the subject's eligibility. Based on the results of the central reading report, the investigators can decide which sub-group subjects belong to by allocating subjects to the more rare type in the ranking of DIE, adenomyosis and endometrioma. If one of the sub-groups has been fully enrolled, subjects will be allocated to the next rarer group.

The primary analyses will be based on measurable lesions (i.e. lesions with a size ≥ 10 mm) at baseline. All lesions with a size < 10 mm will be identified as non-measurable lesions and the existence of such lesions will be recorded at baseline. All lesions, however, will be measured for the segmentation required in the analyses of the exploratory endpoints related to imaging biomarkers (section 7.3.1).

At end-of-treatment / cycle 4, all lesions will be compared to baseline to distinguish new lesion or disappearing lesion, defined as:

- New lesion: a lesion detected at end-of-treatment, regardless of its size, which is not detectable at baseline even during retrospective evaluations
- Disappearing lesion: a lesion detected at baseline, regardless of its size, which is not detectable at end-of-treatment

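### SAP 9.3.4.2 fits a negative binomial to disappearing lesions, a bounded count, drops the protocol's GEE without listing the change, and leaves the offset scale unstated; the intervals tend to be too wide

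*SAP*

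**What the plan says.** SAP 9.3.4.2 defines the outcome lesion by lesion: "The definition of a disappearing lesion is a lesion that is detectable at baseline, but is non-detectable at end-of-treatment". Only women "with at least one lesion of that type that is > 0 mm at baseline" are counted. The count is fitted by negative-binomial regression with a log link, "using the number of lesions of that type as off-set", and treatment differences "will be reported as rate ratios with 95% confidence intervals and corresponding p-values". The section does not write log before the number. It does not say that the number is taken at baseline or whether lesions under 10 mm belong to it, although the definition and the population imply all baseline-detectable lesions. It asks for no robust variance.

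Protocol 9.6.3 planned "repeated measures negative-binomial regression using a GEE approach" for new and disappearing lesions, and said that the regression "will be performed with log link function using the appropriate off-set". The GEE is gone from SAP 9.3.4.2. SAP section 12 lists only the removal of site from the primary model and the 1:1 randomisation list.

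Two further places matter. SAP 9.3.4.1 analyses another yes/no outcome per lesion, shrinkage of at least 5 mm, by logistic regression with GEE because a woman may have several lesions. For adenomyosis, Protocol 7.1.1 has the reader measure "the maximum junctional zone thickness (applicable to diffuse adenomyosis) or the size of the largest focal lesion", so n will often be 1, although SAP 9.2 also allows further adenomyosis lesions.

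**The concern.** A baseline lesion either disappears or it does not, so a woman with n lesions contributes a count between 0 and n. The negative binomial has no upper limit, so fitted proportions can exceed 1. Its variance is the mean plus a non-negative dispersion term and so cannot fall below the mean. For independent lesions with disappearance probability p, the true variance is the mean times (1 − p), which is smaller. The dispersion parameter cannot correct in that direction, and it is barely estimable when n is 1. Without a robust variance, the standard error of the log rate ratio then comes out too large.

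At stake is the precision of a secondary lesion endpoint in a trial with about 24 women planned per sub-group. Intervals that are too wide make it easier to miss an effect. Separately, a programmer has to guess the scale of the offset, and the two possible guesses give different models whenever women differ in lesion number.

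**Working it through.** The documents give no disappearance rate, standard error or power for this endpoint, so there is no stated figure to reproduce. From the documents come the model, the definition, the population, the rate-ratio measure and the 1:1 allocation actually used. Assumed here: p, the within-woman correlation r, and the number of lesions per woman.

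**1. Independent lesions, log offset.** Let each arm have N lesions. The variance of the log proportion in one arm is (1 − p)/(Np) if binomial. The least the negative binomial can give is the Poisson limit, 1/(Np). With equal p in both arms, N cancels and the ratio of standard errors is 1/√(1 − p):

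| p | SE ratio | Excess |
|---|---|---|
| 0.05 | 1.026 | 3% |
| 0.10 | 1.054 | 5% |
| 0.20 | 1.118 | 12% |
| 0.30 | 1.195 | 20% |
| 0.50 | 1.414 | 41% |

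With unequal arms, 20% vs 50%, and 12 women per arm with one lesion each: binomial √(0.8/2.4 + 0.5/6) = 0.645; Poisson limit √(1/2.4 + 1/6) = 0.764; ratio 1.18.

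**2. Correlated lesions.** With m lesions per woman, variance over mean is (1 − p)(1 + (m − 1)r). For m = 3 this equals 1 at r = p/(2(1 − p)), which is 0.06, 0.13 and 0.21 at p = 0.1, 0.2 and 0.3. Above that the count is over-dispersed, and the negative-binomial dispersion has something real to estimate.

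**3. Simulation with the dispersion estimated.** 15 women per arm, true ratio 1, 400 data sets per case, log(n) offset; either 1–4 lesions per woman with probabilities 0.50/0.25/0.15/0.10, or exactly one. Data sets with an arm without events were dropped. The robust column is a log-link Poisson model with sandwich variance and the same offset.

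| Lesions per woman, r | p | Negative binomial: mean SE / empirical SD | 95% CI coverage | Robust coverage |
|---|---|---|---|---|
| 1–4, r = 0 | 0.2 | 0.656/0.627 = 1.05 | 98.5% | 96.0% |
| 1–4, r = 0 | 0.4 | 0.443/0.370 = 1.20 | 98.2% | 95.5% |
| 1–4, r = 0 | 0.6 | 0.355/0.229 = 1.55 | 99.8% | 95.0% |
| 1–4, r = 0.3 | 0.2 | 0.706/0.675 = 1.05 | 99.0% | 98.0% |
| 1–4, r = 0.3 | 0.4 | 0.444/0.417 = 1.06 | 97.2% | 95.8% |
| 1–4, r = 0.3 | 0.6 | 0.356/0.284 = 1.25 | 99.5% | 93.8% |
| one | 0.4 | 0.614/0.551 = 1.11 | 99.0% | 96.5% |
| one | 0.6 | 0.485/0.318 = 1.53 | 100% | 96.8% |

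Over all cases run, including p = 0.1, negative-binomial coverage was 97–100%. At p = 0.1, 10–35% of data sets had an arm without events, so those results are conditional on events in both arms. With 1–4 independent lesions, the mean robust standard error was slightly below the empirical SD of the negative-binomial estimate: 0.574 vs 0.627, 0.338 vs 0.370 and 0.221 vs 0.229 at p = 0.2, 0.4 and 0.6. This is why a small-sample correction is wanted.

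**4. Offset taken literally.** Under a log link, a raw offset n multiplies the expected count by exp(n). Three lesions against one gives exp(2) = 7.4-fold instead of 3-fold; four against one gives exp(3) = 20.1-fold instead of 4-fold. In the 1–4 lesion cases the SD of the log rate ratio rose by 15–82% and coverage was 91.5–97%. With one lesion per woman the offset is constant and the two readings coincide.

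**The case against.** A reader might infer that the SAP prescribes the raw number as offset and that the fitted model will therefore be badly misspecified. The documents do not establish that. The section specifies a log link and reports rate ratios, a combination that implies log(n). Naming the number as the offset is common shorthand for its log. The protocol asks for an appropriate offset, and section 12 declares no change to it. What stands is that neither the scale nor the lesions counted are written down.

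A reader might also infer that the intervals are always too wide, or that inference on this endpoint is unreliable. The factor (1 − p) needs independent lesions of equal risk, and the SAP's own use of GEE in 9.3.4.1 recognises that lesions in one woman are correlated. Modest correlation can remove the under-dispersion, as step 2 shows. With a log offset the error found was conservative, and under-coverage appeared only with the raw offset. The larger figures need common disappearance. The trial was sized for a 33% reduction in lesion size, which says nothing about how often lesions vanish.

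One can add that each woman gives one count per lesion type, so GEE has no repeated counts to handle in the by-type analysis. That is fair as to clustering. Its value here is the robust variance, which remains valid when the variance is below the mean. Finally, moving to logistic GEE changes the effect measure: at 20% vs 50% the rate ratio is 0.5/0.2 = 2.5, but the odds ratio is (0.5/0.5)/(0.2/0.8) = 4.0. It also fails when an arm has no events. Both points stand and shape the fix.

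**Conclusion.** The point holds as a minor one. A bounded x-of-n outcome is given a negative-binomial model with no robust variance stated, and the protocol's GEE is dropped without being listed as a change. With a log offset the rate-ratio intervals tend to be too wide. The excess in standard error is about 3–12% at disappearance of 5–20% and 20–41% at 30–50%, under independence or one lesion per woman, and less with within-woman correlation. All of these rates are assumptions. The offset is an ambiguity to close, not a demonstrated error. The endpoint is secondary and outside the Hochberg procedure, so no primary conclusion changes.

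**What to change.** In SAP 9.3.4.2, choose one of two routes.

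- Keep the rate ratio: restore the GEE (robust) variance of Protocol 9.6.3 with a small-sample correction, and define the offset as log(number of baseline-detectable lesions of that type), saying that lesions under 10 mm count.
- Or analyse disappeared/present per baseline lesion with the logistic GEE of 9.3.4.1, also with a small-sample correction, and note that the odds ratio departs materially from the rate ratio when disappearance is common.

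The first route stays closest to the protocol and keeps the reported measure. Under either, state a fallback for an arm with no events, for example an exact method with the woman as the unit, and list any remaining change from Protocol 9.6.3 in section 12. The cost is SAP wording and a small change to the analysis program; no new data are needed.
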